### 5.1.1. End of Study Definition

The end of study definition is defined as the last visit for the last patient.

## 5.2. Planned Interim Analysis

No interim analysis with alpha spending is planned for this study. An unblinded first-step analysis **may** be performed once all patients in the study have completed the 16-week treatment period as specified in the protocol (week 16 visit or earlier for those patients who are withdrawn prematurely from the study). If performed, this first-step analysis will be considered the final analysis for the primary and secondary efficacy endpoints. A description of the statistical methods to be employed and blinding implications are in Section 10.5.2.4.

## 5.3. Study Committees

### 5.3.1. Independent Data Monitoring Committee

An IDMC, composed of members who are independent from the sponsor and the study investigators, will monitor patient safety by conducting formal reviews of accumulated safety data that will be blinded by treatment group; if requested, the IDMC may have access to the treatment allocation code or any other requested data for the purposes of a risk-benefit assessment.

The IDMC will provide the sponsor with appropriate recommendations on the conduct of the clinical study to ensure the protection and safety of the patients enrolled in the study. The IDMC will also institute any measures that may be required for ensuring the integrity of the study results during the study execution.

All activities and responsibilities of the IDMC are described in the IDMC charter.

## 6. SELECTION, WITHDRAWAL, AND REPLACEMENT OF PATIENTS

### 6.1. Number of Patients Planned

Approximately 330 patients are planned to be enrolled at multiple sites in the US and EU into 3 groups (at 1:1:1 ratio): dupilumab Q2W treatment group (100 mg Q2W or 200 mg Q2W), dupilumab Q4W treatment group (300 mg Q4W), or placebo group (Q2W or Q4W).

### 6.2. Study Population

The study population includes pediatric patients (aged  $\geq 6$  to  $< 12$  years at the time of screening) who have severe AD that cannot be adequately controlled with topical AD medications.

#### 6.2.1. Inclusion Criteria

A patient must meet the following criteria to be eligible for inclusion in the study:

1. Male or female  $\geq 6$  to  $< 12$  years of age at time of screening visit
2. Diagnosis of AD according to the American Academy of Dermatology consensus criteria ([Eichenfield 2003](#)) at screening visit
3. Chronic AD diagnosed at least 1 year prior to the screening visit
4. IGA = 4 at screening and baseline visits
5. EASI  $\geq 21$  at the screening and baseline visits
6. BSA  $\geq 15\%$  at screening and baseline visits
7. Baseline worst itch score weekly average score for maximum itch intensity  $\geq 4$

NOTE: Baseline worst itch average score for maximum itch intensity will be determined based on the average of daily worst itch scores for maximum itch intensity (the daily score ranges from 0 to 10) during the 7 days immediately preceding randomization. A minimum of 4 daily scores out of the 7 days is required to calculate the baseline average score. A complete daily score consists of answers to both questions.

- “What was the worst itch you had today?”
- “What was the worst itch you had last night?”

For patients who do not have at least 4 daily scores reported during the 7 days immediately preceding the planned randomization date, randomization should be postponed until this requirement is met, but without exceeding the 77-day maximum duration for screening plus TCS standardization.

8. With documented recent history (within 6 months before the baseline visit) of inadequate response to topical AD medication(s). For more information, see the note below.

NOTE:

- Inadequate response is defined as failure to achieve and maintain remission or a low disease activity state (comparable to IGA 0=clear to 2=mild) despite treatment with a daily regimen of TCS of medium to high potency ( $\pm$ TCI as appropriate), applied for at least 28 days
  - Patients with documented systemic treatment for AD in the past 6 months are also considered as inadequate responders to topical treatments and are potentially eligible for treatment with dupilumab after appropriate washout.
  - Acceptable documentation includes contemporaneous chart notes that record topical medication prescription and treatment outcome, or investigator documentation based on communication with the patient's treating physician. If documentation is inadequate, potential patients may be offered a course of treatment with a daily regimen of TCS of medium potency, applied for at least 28 days during the screening period (including the 2 weeks TCS standardization period). Patients who demonstrate inadequate response during this period, as defined above, will be eligible for inclusion in the study, as long as they meet other eligibility criteria.
9. At least 11 (of a total of 14) applications of a stable dose of topical emollient (moisturizer) twice daily during the 7 consecutive days immediately before the baseline visit
  10. Willing and able to comply with all clinic visits and study-related procedures
  11. Patient, either alone or with help of parents/legal guardians, as appropriate, must be able to understand and complete study-related questionnaires
  12. Parent or legal guardian must provide signed informed consent. Patients must also provide separate informed assent to enroll in the study, and sign and date either a separate informed assent form (IAF) or the informed consent form (ICF) signed by the parent/legal guardian (as appropriate based on local regulations and requirements)

### 6.2.2. Exclusion Criteria

A patient who meets any of the following criteria will be excluded from the study:

1. Participation in a prior dupilumab clinical study
2. Treatment with a systemic investigational drug before the baseline visit

NOTE: Treatment with a systemic investigational drug refers to treatment received in a clinical study with a drug that is not yet available on the market

3. Treatment with a topical investigational drug within 2 weeks prior to the baseline visit
4. Treatment with crisabarole within 2 weeks prior to the baseline visit

5. History of important side effects of medium-potency-topical corticosteroids (eg, intolerance to treatment, hypersensitivity reactions\*, significant skin atrophy, systemic effects), as assessed by the investigator or patient's treating physician
  - \* If a patient has a history of hypersensitivity reaction to any particular TCS, and/or other ingredient in the particular TCS drug product, the patient can still be randomized if the investigator believes the patient can be safely treated during the study with a different TCS drug product that does not have cross-reactivity to the drug product that caused the hypersensitivity.
6. Treatment with a TCI within 2 weeks prior to the baseline visit
7. Having used any of the following treatments within 4 weeks before the baseline visit, or any condition that, in the opinion of the investigator, is likely to require such treatment(s) during the first 4 weeks of study treatment:
  - a. Immunosuppressive/immunomodulating drugs (eg, systemic corticosteroids, cyclosporine, mycophenolate-mofetil, interferon gamma, Janus kinase inhibitors, azathioprine, methotrexate, etc)
  - b. Phototherapy for AD
8. Treatment with biologics, as follows:
  - a. Any cell-depleting agents including but not limited to rituximab: within 6 months before the baseline visit, or until lymphocyte and CD 19+ lymphocyte count returns to normal, whichever is longer
  - b. Other biologics: within 5 half-lives (if known) or 16 weeks before the baseline visit, whichever is longer
9. Treatment with a live (attenuated) vaccine within 4 weeks before the baseline visit

NOTE: For patients who have vaccination with live, attenuated vaccines planned during the course of the study (based on national vaccination schedule/local guidelines), it will be determined, after consultation with a pediatrician, whether the administration of vaccine can be postponed until after the end of study, or preponed to before the start of the study, without compromising the health of the patient:

  - Patients for whom administration of live (attenuated) vaccine can be safely postponed would be eligible to enroll into the study.
  - Patients who have their vaccination preponed can enroll in the study only after a gap of 4 weeks following administration of the vaccine.
10. Planned or anticipated use of any prohibited medications and procedures during study treatment
11. Body weight <15 kg at baseline

12. Initiation of treatment of AD with prescription moisturizers or moisturizers containing additives such as ceramide, hyaluronic acid, urea, or filaggrin degradation products during the screening period (patients may continue using stable doses of such moisturizers if initiated before the screening visit)
13. Regular use (more than 2 visits per week) of a tanning booth/parlor within 8 weeks of the baseline visit
14. Active chronic or acute infection requiring treatment with systemic antibiotics, antivirals, antiprotozoals, or antifungals within 2 weeks before the baseline visit,  
NOTE: patients may be rescreened after infection resolves
15. Established diagnosis of a primary immunodeficiency disorder (eg, severe combined immunodeficiency, Wiskott Aldrich Syndrome, DiGeorge Syndrome, X-linked Agammaglobulinemia, common variable immunodeficiency), or secondary immunodeficiency. Patients suspected to have immunodeficiency based on their clinical presentation (history of invasive opportunistic infections eg, tuberculosis, other mycobacterial infections, histoplasmosis, listeriosis, coccidioidomycosis, pneumocystosis, chronic mucocutaneous candidiasis, etc or otherwise recurrent infections of abnormal frequency or prolonged duration suggesting an immune-compromised status, as judged by the investigator)
16. History of past or current tuberculosis or other mycobacterial infection  
Note: Irrespective of status of treatment or infection resolution. Tuberculosis testing will be performed on a country by country basis according to local guidelines if required by regulatory authorities or ethic committees.
17. Known history of human immunodeficiency virus (HIV) infection or HIV seropositivity at the screening visit
18. With an established diagnosis of hepatitis B viral infection at the time of screening or is positive for hepatitis B surface antigen (HBsAg) or hepatitis B core antibody (HBcAb) at the time of screening  
NOTE: Patients who have gained immunity for hepatitis B virus infection after vaccination (patients who are HBsAg negative, hepatitis B surface antibody [HBsAb] positive, and HBcAb negative) are eligible for the study.
19. With an established diagnosis of hepatitis C viral infection at the time of screening or is positive for hepatitis C antibody at the screening visit
20. On current treatment for hepatic disease including but not limited to acute or chronic hepatitis, cirrhosis, or hepatic failure, or has evidence of liver disease as indicated by persistent (confirmed by repeated tests  $\geq 2$  weeks apart) elevated transaminases (alanine aminotransferase [ALT] and/or aspartate aminotransferase [AST]) more than 3 times the upper limit of normal (ULN) during the screening period

21. Presence of any 1 or more of the following abnormalities in laboratory test results at screening:

- Platelets  $\leq 100 \times 10^3/\mu\text{L}$
- Neutrophils  $< 1.5 \times 10^3/\mu\text{L}$
- Creatine phosphokinase (CPK)  $> 5 \times \text{ULN}$
- Serum creatinine  $> 1.5 \times \text{ULN}$

NOTE: If an abnormal value is detected at screening, a repeat test should be performed to confirm the abnormality. Only if the repeat test confirms the abnormality, the patient would be categorized as a screen failure.

22. Presence of skin comorbidities that may interfere with study assessments. This includes, but is not limited to, conditions like scabies, seborrheic dermatitis, cutaneous T cell lymphoma, psoriasis, etc.
23. History of malignancy before the baseline visit
24. Diagnosed active endoparasitic infections; suspected or high risk of endoparasitic infection, unless clinical and (if necessary) laboratory assessment have ruled out active infection before randomization
25. Severe concomitant illness(es) that, in the investigator's judgment, would adversely affect the patient's participation in the study. Examples include, but are not limited to patients with short life expectancy, patients with uncontrolled diabetes (hemoglobin A1c  $\geq 9\%$ ), patients with cardiovascular conditions (eg, Class III or IV cardiac failure according to the New York Heart Association classification), severe renal conditions (eg, patients on dialysis), hepato-biliary conditions (eg, Child-Pugh class B or C), neurological conditions (eg, demyelinating diseases), active major autoimmune diseases (eg, lupus, inflammatory bowel disease, rheumatoid arthritis, etc.), other severe endocrinological, gastrointestinal, metabolic, pulmonary, or lymphatic diseases. The specific justification for patients excluded under this criterion will be noted in study documents (chart notes, case report forms [CRF], etc).
26. Any other medical or psychological condition including relevant laboratory abnormalities at screening that, in the opinion of the investigator, suggest a new and/or insufficiently understood disease, may present an unreasonable risk to the study patient as a result of his/her participation in this clinical trial, may make patient's participation unreliable, or may interfere with study assessments. The specific justification for patients excluded under this criterion will be noted in study documents (chart notes, CRF, etc.).
27. Planned major surgical procedure during the patient's participation in this study
28. Patient or his/her immediate family is a member of the dupilumab investigational team
29. Patient is female who is pregnant, breastfeeding, or planning to become pregnant or breastfeed during the study
30. Patients who are committed to an institution by virtue of an order issued either by the judicial or the administrative authorities

31. Patient is female of childbearing potential\* and sexually active, who is unwilling to use highly effective methods of contraception prior to the initial dose, during the study and for at least 12 weeks after the last dose of study drug. Highly effective contraceptive measures include stable use of combined (estrogen and progestogen containing) hormonal contraception (oral, vaginal, transdermal) or progestogen-only hormonal contraception (oral, injectable, implantable) associated with inhibition of ovulation initiated 2 or more menstrual cycles prior to screening; intrauterine device (IUD); intrauterine hormone-releasing system (IUS); bilateral tubal ligation; vasectomized partner; and or sexual abstinence\*\*.

\* For the purpose of this study, any female who has had her first menstrual period (menarche) and is sexually active will be considered to be of childbearing potential. Female patients who are not of childbearing potential at the start of the study but have the onset of menarche during the course of the study and are sexually active will also have to follow adequate birth control methods to continue participation in the study.

\*\* Sexual abstinence is considered a highly effective method only if defined as refraining from heterosexual intercourse during the entire period of risk associated with the study treatments. The reliability of sexual abstinence needs to be evaluated in relation to the duration of the clinical trial and the preferred and usual lifestyle of the subject.

NOTE: Periodic abstinence (eg, calendar, ovulation, symptothermal, post-ovulation methods), declaration of abstinence for the duration of a study, and withdrawal are not acceptable methods of contraception.

### 6.3. Premature Withdrawal from the Study

A patient has the right to withdraw from the study at any time, for any reason, and without repercussion. The parent/caregiver has the right to withdraw permission to have the patient participate in the study at any time, for any reason, and without repercussion.

The investigator and sponsor have the right to withdraw a patient from the study in the event of an intercurrent illness, AE, treatment failure, protocol violation, cure, and for administrative, or other reasons. An excessive rate of withdrawals would render the study uninterpretable; therefore, unnecessary withdrawal of patients should be avoided.

Patients who withdraw prematurely from the study will be asked to complete study assessments per Section 8.1.

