During the treatment period, patients will have weekly in-clinic visits through week 4, and then in-clinic visits Q4W through week 16 with weekly telephone visits in between the in-clinic visits. Parents/caregivers will be trained on injecting study drug during in-clinic visit 3 (day 1), visit 5 (week 2), and visit 7 (week 4) (this only applies to patients who will receive Q2W treatment during the study). During weeks in which no in-clinic visit is scheduled, the parent/caregiver will administer study drug to the patient. In case the parent/caregiver does not want to administer study drug to patient, they may have the clinic staff administer all the study drug injections in the clinic. Safety, laboratory, and clinical assessments will be performed at specified clinic visits, as noted in [Table 1](#). The end of treatment period visit will occur at week 16, two weeks after the last dose of study drug for patients randomized to the Q2W treatment group or placebo Q2W group, and 4 weeks after the last dose of study drug for patients randomized to the Q4W treatment or placebo Q4W group. The co-primary endpoints will be assessed at this visit. If patients prematurely discontinue study treatment, the patients will be encouraged to stay in the study to have data collected at all remaining scheduled visits until completion of the planned end of study visit. Patients who participate in the study may subsequently be eligible to participate in an OLE study. All patients will be offered the opportunity to screen for entry into the OLE study at the end of the treatment period (week 16).

Patients who decline to enroll in the OLE study or those who fail eligibility criteria for the OLE study will have a 12-week follow-up period. For these patients, after week 16, follow-up visits will occur every 4 weeks from week 20 to week 28. During the follow-up period, patients will be monitored for safety and tolerability and have laboratory and clinical assessments as noted in [Table 2](#).

Figure 2: Study Flow Diagram

D = study day; W = study week

Note: The length of the screening period is not fixed, but the screening period and TCS standardization must not exceed 77 days. The length of the TCS standardization period is fixed at 14 days.

 For patients who enter the OLE, week 16 is the end of study.

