### 7.3. Rescue Treatment

Rescue treatment for AD may be provided to patients during the study. Investigators will be required to perform an IGA assessment prior to starting rescue treatment and initiate rescue treatment only in patients who either have an IGA score = 4, or have intolerable symptoms. If possible, investigators are encouraged to consider rescue initially with topical treatment (eg, high-potency TCS) and to escalate to systemic medications only for patients who do not respond adequately after at least 7 days of topical treatment. Patients may continue study treatment if rescue consists of topical medications. The use of very-high-potency or superpotent TCS is prohibited in this study, even as rescue treatment, as their use is not recommended in patients under 12 years of age. Very-high-potency topical corticosteroids include:

- Betamethasone dipropionate augmented 0.05% ointment
- Clobetasol propionate 0.05% solution, foam, cream or ointment
- Diflorasone diacetate 0.05% ointment
- Halobetasol propionate 0.05% cream or ointment

Patients who receive systemic corticosteroids or systemic non-steroidal immunosuppressive drugs (eg, cyclosporine, methotrexate, mycophenolate-mofetil, azathioprine, etc) as rescue medication during the study will be discontinued permanently from the study drug. All patients will be asked to complete the scheduled study visits and assessments whether or not they complete study treatment and whether or not they receive rescue treatment for AD. Investigators should make every attempt to conduct efficacy and safety assessments (eg, disease severity scores, safety laboratory tests) immediately before administering any rescue treatment. An unscheduled visit may be used for this purpose, if necessary. For the purpose of efficacy analysis, patients who receive rescue treatment during the study will be considered treatment failures.

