#### 10.5.2.1. Primary Efficacy Analysis

The Cochran-Mantel-Haenszel test adjusted by randomization strata (baseline weight group and region) will be used for analyzing the percentage of patients with IGA 0 or 1 at week 16 or percentage of patients with EASI-75 at week 16. The Mantel-Fleiss (MF) criterion will be checked, and if it is not met, sensitivity analyses including each stratification factor separately in CMH test will be conducted.

All efficacy data regardless if the patient is on the study treatment or discontinues the study treatment but remains in the study will be used for analysis. Specifically, if a patient stays in the study until the end of the planned placebo-controlled treatment period, all efficacy data collected up to the planned end of treatment visit will be included in the primary analysis regardless if the patient is on treatment or not.

To account for the impact of rescue treatment on the efficacy effect: For the primary efficacy endpoints (which are binary efficacy endpoints), if rescue treatment is used (see Section 7.3), the patient will be specified as a nonresponder from the time the rescue is used.

If a patient withdraws from study, this patient will be counted as a nonresponder for endpoints after withdrawal.

Sensitivity analysis using the last observation carried forward (LOCF) approach to determine patient's status at week 16 will be conducted to assess the robustness of the primary efficacy analysis with regards to handling of missing data. The efficacy data will be set to missing after rescue treatment is used, then the LOCF method will be used to determine patients' status at week 16.

In addition, the Cochran-Mantel-Haenszel method adjusted by randomization strata will also be performed on all observed data regardless if rescue treatment is used. A patient with missing data will be counted as a non-responder. Other sensitivity analyses may be conducted.

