5.7.1. Analysis of Primary Efficacy Variable

The Cochran-Mantel-Haenszel (CMH) test adjusted by randomization strata (baseline weight group (<30 kg or ≥30kg) and region (North America or Europe) will be used for the analysis of percentage of patients with IGA 0 or 1 at week 16 or percentage of patients with EASI-75 at week 16. The Mantel-Fleiss (MF) criterion will be performed, and if it is not met while using the option CMH (MF) in SAS procedure PROC PREQ, sensitivity analyses including each factor separately in CMH test will be conducted.

All efficacy data, regardless of whether the patient remains on study treatment or discontinues the study treatment but remains in the study, will be used for analysis. Specifically, if a patient stays in the study until the end of the study planned placebo-controlled treatment period, all efficacy data collected up to the study planned end of treatment visit will be included in the primary analysis, regardless of whether the patient is on treatment or not.

Handling of dropouts or adjudicated rescue treatment or missing value for the binary response variables as the primary analysis

- If a patient withdraws from the study, this patient will be counted as a non-responder for the time points after withdrawal.
- To account for the impact of rescue treatment on the efficacy effect: if rescue treatment is used (see Section 4.3 for rescue treatment), the patient will be specified as a non-responder from the time the rescue treatment is used.
- If the patient has the missing value at week 16, then it will be counted as a non-responder at week 16.

Sensitivity analyses

1. Post-baseline Last Observation Carried Forward (LOCF) approach after censoring for rescue treatment use or study withdrawal to determine patient's status at week 16 will be conducted to assess the robustness of the primary efficacy analysis with regards to handling of missing data.
2. All observed data, regardless if rescue treatment is used or data is collected after withdrawal from study treatment will be included for analysis. Patients with missing value will be counted as non-responder.

The primary efficacy analyses will be performed on the FAS, which will be considered as the primary analysis. Evaluation of primary and co-primary endpoints in the mFAS and PPS will be considered as sensitivity analyses.

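### Protocol 6.3 allows withdrawal from the study for cure or protocol violation, so a child withdrawn as cured before week 16 is normally scored as a week 16 non-responder

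*Protocol*

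**What the plan says.** Protocol 6.3 reserves to the investigator and sponsor a right to "withdraw a patient from the study in the event of an intercurrent illness, AE, treatment failure, protocol violation, cure", and adds administrative and other reasons. It does not define cure. It also says that "unnecessary withdrawal of patients should be avoided", and it asks withdrawn patients to complete the assessments in Section 8.1, where the early termination visit includes IGA and EASI.

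For the binary endpoints the scoring rule takes no account of the reason. Protocol 10.5.2.1: "If a patient withdraws from study, this patient will be counted as a nonresponder for endpoints after withdrawal". SAP 5.7.1: "If a patient withdraws from the study, this patient will be counted as a non-responder for the time points after withdrawal". The SAP adds: "If the patient has the missing value at week 16, then it will be counted as a non-responder at week 16". The first sensitivity analysis is a "Post-baseline Last Observation Carried Forward (LOCF) approach after censoring for rescue treatment use or study withdrawal". The second uses all observed data and still scores a missing value as non-response.

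Elsewhere the plan tries to keep children under observation. When study treatment stops early, Protocol 5.1 says "the patients will be encouraged to stay in the study to have data collected at all remaining scheduled visits". Protocol 7.3 says "All patients will be asked to complete the scheduled study visits and assessments whether or not they complete study treatment", and applies this to rescued patients too. Protocol 7.4.2 asks children who stop drug but stay in the study to attend the remaining visits.

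**The concern.** Clear or almost clear skin is the IGA endpoint. If a child reaches it early and is withdrawn from the study as cured, the primary analysis records the opposite of what was observed. Protocol 7.2 already manages clearance within the study: topical steroid stops at IGA 0 and restarts if lesions return. The plan itself therefore does not treat clearance as a reason to stop observing.

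Protocol violation raises a related problem. The full analysis set is all randomized patients, and violations are meant to be handled by the per protocol set (Protocol 10.3.1, SAP 3.1). The preliminary list in Protocol Appendix 3 includes site-level matters such as expired laboratory kits and late SAE reports. Ending follow-up for such a violation removes outcome data from the primary set with no analytic gain.

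What is at stake is avoidable missing data in the co-primary endpoints. Part of it depends on outcome, and cure is more likely to be declared on an effective drug than on placebo.

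**Working it through.** **1. Following one cured child through the rules**

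| Time of withdrawal | Primary binary analysis | LOCF sensitivity | All-observed sensitivity |
|---|---|---|---|
| Before day 100 | Non-responder at week 16 | Last response carried forward, so can be a responder | Missing, so non-responder |
| Day 100 or later, no scheduled week 16 visit, early termination visit in days 100 to 127 | Unclear: SAP 6.4 maps that value to week 16, while SAP 5.7.1 scores time points after withdrawal as non-response | Can be a responder | Depends on the same mapping |
| After the week 16 assessment | Observed result kept | Observed result kept | Observed result kept |

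EASI and itch as continuous endpoints are multiply imputed (SAP 5.7.2), so there the child is not scored as a failure.

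**2. Reproducing the plan's power**

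Inputs from Protocol 10.2: two-sided 5% level, 80 per group; IGA 0/1 of 28% (Q2W), 22% (Q4W) and 5% (placebo); EASI-75 of 68%, 62% and 17%.

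Power = Φ{ [ |p1 − p2| − 1.96·√(2p̄(1 − p̄)/n) ] / √[ (p1(1 − p1) + p2(1 − p2))/n ] }, with p̄ = (p1 + p2)/2.

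This gives 98.0%, 89.0%, >99.9% and >99.9%, against the stated 97%, 87%, 99% and 99%. Exact power of Fisher's test gives 97.9% and 87.2% for the two IGA comparisons. The plan's figures reproduce within 2 points. The formula is slightly generous for Q4W.

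**3. Size of the effect of cure withdrawals**

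The documents give no rate of withdrawal for cure. Let c be the assumed share of would-be IGA responders in a dupilumab arm who are withdrawn as cured before week 16 and scored as non-responders. Placebo stays at 5%, with n = 110 per arm (the current total of 330). The scored rate is p1(1 − c), and the number of children lost is 110·p1·c.

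| c | Children lost, Q2W / Q4W | Difference, Q2W / Q4W (points) | Power, Q2W / Q4W |
|---|---|---|---|
| 0 | 0 / 0 | 23.0 / 17.0 | 99.7% / 96.3% |
| 5% | 1.5 / 1.2 | 21.6 / 15.9 | 99.5% / 94.5% |
| 10% | 3.1 / 2.4 | 20.2 / 14.8 | 99.0% / 92.0% |
| 20% | 6.2 / 4.8 | 17.4 / 12.6 | 96.8% / 84.4% |

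Example, Q4W at c = 20%: 0.22 × 0.8 = 0.176 and p̄ = 0.113. The pooled term is 1.96 × √(2 × 0.113 × 0.887/110) = 0.0837. The denominator is √[(0.176 × 0.824 + 0.05 × 0.95)/110] = 0.0418. Then z = (0.126 − 0.0837)/0.0418 = 1.01, so power is 84.4%.

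If the same share were lost from placebo, c = 10% would give differences of 20.7 and 15.3 points, with power 99.3% and 94.0%.

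**The case against.** The case against is substantial. Section 6.3 reserves a discretion; it directs no withdrawal and discourages unnecessary ones. Atopic dermatitis is described in Protocol section 1 as chronic and relapsing, treatment lasts 16 weeks, and an open-label extension is offered at week 16. Cure withdrawals should therefore be rare. Any such loss concentrated on dupilumab shrinks the estimated difference, so it works against the drug. A gap between LOCF and the primary analysis would help to reveal the problem, and discontinuations are reported by reason (Protocol 10.4, SAP 5.4). All of this stands and limits the size of the point. It does not remove the mismatch, because cure remains a listed reason and the scoring rule has no exception for it.

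Three stronger readings are tempting, and the documents do not support them.

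- A reader might infer that every withdrawn child becomes a week 16 failure. The rule reaches only time points after withdrawal, follow-up runs to week 28, and an early termination value may serve as the week 16 value.
- A reader might infer that withdrawal for treatment failure is also mis-scored. Non-response is the consistent score on the binary endpoints, and rescued children are non-responders from rescue onward anyway. For EASI and itch, SAP 5.7.2 adds a worst-observation-carried-forward analysis. What remains is that 6.3 permits withdrawal for treatment failure while 7.3 asks children it classes as treatment failures to complete their visits.
- A reader might suppose many such losses. Ten of 31 Q2W responders would give 21/110 = 19.1% and power of about 90.0%, but that is 10/31 = 32% of responders, and nothing in the documents points to such a rate.

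**Conclusion.** The point holds in limited form, at minor severity. As written, a child withdrawn as cured before day 100 is a week 16 non-responder on IGA 0/1 and EASI-75. From day 100 the SAP leaves the result open when the scheduled visit is absent and an early termination value exists. Withdrawal for protocol violation can discard primary-set data without need.

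On the assumed 5% to 20% of dupilumab responders, the IGA difference falls by 1.4 to 5.6 points (Q2W) and 1.1 to 4.4 points (Q4W). Q2W power stays at 96.8% or more. Q4W power stays above the 90% stated in Protocol 10.2 at a 10% loss (92.0%) and drops below it at 20% (84.4%). These figures rest on an assumed rate, placebo fixed at 5%, 110 per arm, the protocol's adult-based response rates and a normal approximation. The expected direction is conservative, so this is a matter of accuracy and avoidable missing data, not of a false claim of efficacy.

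**What to change.** - **Protocol 6.3:** remove cure as a reason for study withdrawal. State that neither clearance nor a protocol violation by itself ends data collection, including under the administrative and other reasons, which would otherwise permit the same withdrawals. Except for violations that amount to invalid or withdrawn consent or assent. State that these children are asked to attend the week 16 IGA, EASI and itch assessments. The family's right to withdraw is unchanged.
- **Protocol 6.3 with 7.3 and 7.4.2:** reconcile the treatment-failure wording, without changing any study-drug stopping rule.
- **SAP 5.7.1 and 6.4:** state whether the withdrawal rule or the early termination window prevails for a value on days 100 to 127.

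The cost is a few sentences, and a few more children attending visits already scheduled for them.
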